#### Methodology:

- **Study Design:** The risk factors of aspergillus pneumonia were compared between aspergillus colonization group and aspergillus pneumonia group.
- **Participants:** Patients with chronic lung disease were identified as positive for Aspergillus fumigatus through sputum microscopy. According to diagnostic criteria, patients diagnosed with IPA and CPA and were assigned to the Aspergillosis pneumonia group, while the remaining patients were included in the Aspergillus colonization group. Then, Risk factors for aspergillus pneumonia, invasive pulmonary aspergillus disease, and chronic pulmonary aspergillus disease, such as the use of high-dose corticosteroids, inhaled corticosteroids, and the extent of damage to basic lung structures, were identified by comparing the aspergillus colonization group with the aspergillus infection group.
- **Procedures:**

- Patients diagnosed with chronic lung disease were screened out who were qualified by sputum microscopy and positive for aspergillus in sputum culture.
- The chest high-resolution computed tomography (HRCT), serum Aspergillus specific IgG antibody, serum aspergillus IgM antibody and serum GM test were performed.
- The risk factors of aspergillus infection group and aspergillus colonization group were compared.
- **Ethics Approval:** Granted by the Medical Ethics Committee of Sichuan Provincial People's Hospital.

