### **Statistical Analysis Plan**

#### **Data Analysis Strategy:**

1. **Descriptive Statistics:**
  - Summarize participant characteristics using means and standard deviations for continuous variables and frequencies for categorical variables.
2. **Identify independent risk factors:**
  - Independent risk factors for aspergillus infection were determined by multivariate logistic regression analysis.
3. **Comparison Between Groups:**
  - The area under ROC curve (AUC) was used to evaluate the classification effect of the binary classification model among Aspergillus pneumonia group, IPA group and CPA group.
4. **Threshold Analysis:**
  - Specific cut-off values for Aspergillus specific IgG antibody  $\times$  lung structural injury image score was determined to maximize diagnostic accuracy, focusing on sensitivity, specificity, and Youden index.

**Software:** Statistical analysis will be conducted using SPSS version 25.0 or a similar statistical package.

**Ethical Considerations:** Data will be anonymized to protect patient confidentiality, with all procedures carried out in accordance with the Declaration of Helsinki.

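### Item 3 of the SAP appears to compute the logistic model's AUC in the same patients used to fit it, with no internal validation, so the reported AUC will be biased upward.

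*Combined protocol and SAP*

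**What the plan says.** Item 2 of the Data Analysis Strategy states: "Independent risk factors for aspergillus infection were determined by multivariate logistic regression analysis". Item 3 then states: "The area under ROC curve (AUC) was used to evaluate the classification effect of the binary classification model among Aspergillus pneumonia group, IPA group and" (the sentence ends with the CPA group).

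The Participants paragraph of the Methodology describes one pool of patients. Those who meet the diagnostic criteria form the case group ("patients diagnosed with IPA and CPA and were assigned to the Aspergillosis pneumonia group"), and "the remaining patients were included in the Aspergillus colonization group". IPA and CPA are therefore subsets of the pneumonia group. The same paragraph sets out to find "Risk factors for aspergillus pneumonia, invasive pulmonary aspergillus disease, and chronic pulmonary aspergillus disease", giving examples: "such as the use of high-dose corticosteroids, inhaled corticosteroids, and the extent of damage to basic lung structures". The Procedures add further measurements: "serum Aspergillus specific IgG antibody, serum aspergillus IgM antibody and serum GM test were performed".

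The documents do not give group sizes, a final predictor list, a selection rule, a significance level, a method for an AUC interval or test, or any validation sample, resampling or penalization. They do not say whether one model or three will be fitted.

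**The concern.** A logistic model's coefficients are chosen to separate the patients it was fitted to. Scoring those same patients and computing the AUC measures fit, not how well the model would classify new patients. Some apparent discrimination appears even when no predictor is related to the outcome.

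Two conclusions are at stake. One is that the risk-factor model classifies aspergillosis, because item 3 is the only evaluation of the model that the SAP states. The other is any comparison of AUCs among pneumonia, IPA and CPA. Item 3 is a between-group comparison by its title, and the amount of bias depends on the size of the case group.

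This is separate from the cut-off in item 4. The product of IgG and image score has no fitted coefficients, so correcting item 4 would leave item 3 as it is.

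**Working it through.** The plan states no AUC, sample size or power, so it has no figure of its own to reproduce.

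**Inputs.** From the documents: at least three candidate factors, given as examples, and six if IgG, IgM and GM are added. Assumed: 90 colonized patients; 20, 40 or 60 cases; independent normal predictors, all entered.

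**1. Apparent AUC when nothing predicts.** With k noise predictors, the squared standardized distance between the groups along the fitted score behaves approximately as chi-square(k) × (1/n1 + 1/n0), and AUC = Φ(distance/√2). The mean apparent AUC is therefore close to Φ(c × √[(1/n1 + 1/n0)/2]), where c is the mean of a chi variable with k degrees of freedom: 1.596 for k = 3 and 2.350 for k = 6.

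| Cases (n1) | √[(1/n1 + 1/90)/2] | k = 3 | k = 6 |
|---|---|---|---|
| 20 | 0.1748 | Φ(0.279) = 0.610 | Φ(0.411) = 0.659 |
| 40 | 0.1344 | Φ(0.214) = 0.585 | Φ(0.316) = 0.624 |
| 60 | 0.1179 | Φ(0.188) = 0.575 | Φ(0.277) = 0.609 |

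The true value is 0.50 throughout. Simulation of fitted logistic models agrees: for k = 3, 0.61 with 20 cases and 0.58 with 60. In a separate set of simulations (20 to 80 cases, 50 to 200 colonized), noise models scored on fresh patients averaged 0.496 to 0.504. The excess therefore comes from reusing the fitting data.

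**2. Optimism when there is real signal.** With a best achievable AUC of 0.70 and k = 3, simulation gives:
- 60 cases: apparent 0.712, in new patients 0.690, difference 0.022.
- 20 cases: apparent 0.725, in new patients 0.678, difference 0.047.

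**3. Comparison across groups, no true effect** (IPA 20, CPA 40, colonized 100, k = 3):
- Separate models: mean AUC 0.611 / 0.584 / 0.574 for IPA / CPA / pooled. The smallest group ranks first in 66% of samples (71% with k = 5, 77% with k = 8). With similar sizes, 30 and 35, it ranks first in only 54 to 57%.
- One pooled model scored in each subgroup: 0.577 / 0.574 / 0.575. The smaller group ranks first in about half of samples (49 to 52% over the settings tried).

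**4. If the AUC were also judged against 0.5.** The SAP states no such test. A standard ROC interval takes the score as given in advance, so in effect a chi-square(k) statistic is judged against a one-degree-of-freedom limit: P(chi-square(3) > 3.84) = 28%. Simulation with three noise predictors gives 25 to 35% over 20 to 80 cases and 50 to 200 colonized. A truly fixed single marker gives 4.8 to 6.1%.

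**5. Does selection help?** No. Screening 10 noise candidates at univariate p < 0.05 (20 to 80 cases, 100 colonized) still gives a mean apparent AUC of 0.542 to 0.576.

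**The case against.** **The model may not be the item 2 regression.** Item 3 does not name its model. It is the only ROC step in the SAP, and item 4 chooses a Youden cut-off for the product of IgG and image score. If item 3 concerns that product, no coefficients are fitted and this optimism does not arise. That stands as an ambiguity. But the SAP calls the object a binary classification model, and the item 2 regression is the only one it names, so the regression remains the natural reading.

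**The plan states no AUC test.** A reader might infer that the SAP treats the fitted score as a fixed marker and will declare success when an interval excludes 0.5. The documents do not support that: no interval, comparison with 0.5 or significance level appears. The false-positive rate in step 4 of the working is therefore conditional on an analyst adding such a test. The bias in the AUC itself needs no test.

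**The smallest group need not look best.** A reader might infer that IPA or CPA, whichever is rarer, will come out on top. That needs a separate model for each group and clearly unequal sizes, and even then it is a tendency. The Methodology lists three outcomes, but item 2 describes one analysis, and one pooled model removes the effect.

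**Size and scope.** Much larger figures can be produced with ten predictors, but nothing in the documents supports ten. With three factors and real signal the optimism is small. The stated objective, identifying risk factors, rests on item 2, whose coefficients item 3 does not alter. Both points stand and limit the weight of the concern to a performance claim.

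**Conclusion.** The concern holds in a limited form. On its natural reading, item 3 reports an apparent AUC without correction, and this is biased upward. Where no factor matters, the inflation averages about 0.08 to 0.11 with the three named factors and about 0.11 to 0.16 with six. With real signal (best achievable AUC 0.70) and three factors it is about 0.02 to 0.05. It is largest in the smallest case group. A distorted ranking of pneumonia, IPA and CPA follows only if a model is refitted for each.

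These figures rest on assumed group sizes, independent normal predictors and all candidates being entered. The direction of the bias does not depend on the assumed sizes; the amount does. The change is worth making because it is cheap and item 3 is the model's only stated evaluation. The concern does not invalidate the risk-factor analysis.

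**What to change.** In item 3:

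- State that the model is the item 2 regression, if that is intended, and whether it is refitted for pneumonia, IPA and CPA or fitted once and scored in each group.
- List the candidate predictors and any selection rule in item 2.
- Report a bootstrap optimism-corrected AUC (at least 500 resamples) or a repeated cross-validation AUC, repeating any variable selection and the refit each time. Give a bootstrap interval and show the apparent AUC alongside.
- Do not rank the three groups on apparent AUCs, and compare corrected values with caution. The correction leaves some optimism: in simulation with no effect and three predictors, the corrected AUC averaged 0.538 with 20 cases and 0.522 with 60, against a true 0.50.
- Judge whether the model has any signal by the likelihood-ratio test of the whole listed candidate set, not by a ROC interval against 0.5. With no effect, this test rejected in about 5% of simulated studies with three predictors, but in 7.7% with ten predictors and 20 cases, so the list should be kept short for small groups.

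The cost is some SAP wording, agreement on the candidate list and a little programming; the SAP already permits software other than SPSS. No new patients or data are needed. The reported AUCs will be lower, most of all in the smallest group.

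### The IgG × image-score cut-off is chosen to maximise accuracy in one cohort with no internal validation specified, so its reported accuracy will on average be too high for new patients

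*Combined protocol and SAP*

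**What the plan says.** Four places in the combined document bear on this.

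- **SAP, Data Analysis Strategy, item 4.** The cut-off for the IgG × image-score product is to be "determined to maximize diagnostic accuracy, focusing on sensitivity, specificity, and Youden index". No value is fixed in advance, so the cut-off is estimated from the study data.
- **Protocol, Methodology, Participants.** There is one set of Aspergillus-positive patients. Those diagnosed with IPA or CPA form the pneumonia group, "while the remaining patients were included in the Aspergillus colonization group".
- **SAP, item 3.** The AUC is used to assess "the classification effect of the binary classification model among Aspergillus pneumonia group, IPA group and CPA group". The model is not defined. It could be the logistic model of item 2 or the IgG × image-score product.
- **SAP, item 2.** "Independent risk factors for aspergillus infection were determined by multivariate logistic regression analysis". The number of candidate predictors and any selection method are not stated.

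Neither document mentions a hold-out sample, cross-validation, bootstrap, optimism correction or external cohort. Neither gives a sample size, group sizes or an expected AUC.

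**The concern.** A cut-off picked because it gives the best observed accuracy fits the chance features of the sample as well as the real separation between groups. Accuracy at that cut-off in the same patients is therefore biased upward on average. The bias grows as groups shrink. IPA and CPA are subsets of the pneumonia group, so separate cut-offs for them would be affected more.

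Readers of a diagnostic cut-off will naturally take its sensitivity and specificity as what to expect in other patients, and on average those patients would show less. The point concerns the threshold, and the AUC only if that AUC comes from a model fitted in these data.

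**Working it through.** **No planned figure to reproduce.** The documents state no sample size, AUC or accuracy target. The direction can be shown in general; the size needs assumptions.

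**Direction.** Let J(c) = sensitivity(c) + specificity(c) − 1 be the true Youden index at cut-off c, Ĵ(c) its value in the sample, and ĉ the cut-off that maximises Ĵ. For any fixed c, Ĵ(c) is unbiased. Hence

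E[Ĵ(ĉ)] = E[max Ĵ(c)] ≥ max J(c) ≥ E[J(ĉ)].

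The reported value is on average at least the best achievable value, and performance in new patients at the chosen cut-off is on average at most that value.

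**Assumptions for size.** The marker is normal with equal variance in both groups, with AUC 0.70 or 0.80. Group sizes (cases/colonised) run from 15/30 to 200/200, with 5,000 replicates per setting. The separation is δ = √2·Φ⁻¹(AUC) and the best achievable Youden index is 2Φ(δ/2) − 1:

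- AUC 0.70: δ = 1.414 × 0.524 = 0.742; 2Φ(0.371) − 1 = 0.289.
- AUC 0.80: δ = 1.414 × 0.842 = 1.190; 2Φ(0.595) − 1 = 0.448.

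**Mean Youden index at the selected cut-off**

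| Cases/colonised | AUC | Apparent | True | Excess | Bootstrap-corrected |
|---|---|---|---|---|---|
| 15/30 | 0.70 | 0.41 | 0.26 | 0.15 | 0.31 |
| 30/60 | 0.70 | 0.37 | 0.27 | 0.10 | 0.29 |
| 100/100 | 0.70 | 0.34 | 0.28 | 0.06 | 0.29 |
| 200/200 | 0.70 | 0.32 | 0.28 | 0.04 | 0.29 |
| 15/30 | 0.80 | 0.55 | 0.42 | 0.13 | 0.47 |
| 30/60 | 0.80 | 0.52 | 0.43 | 0.09 | 0.46 |
| 100/100 | 0.80 | 0.49 | 0.44 | 0.05 | 0.45 |
| 200/200 | 0.80 | 0.48 | 0.44 | 0.04 | 0.45 |

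The excess is apparent minus true, from the rounded values. The corrected column comes from a smaller run of 400 datasets with 200 resamples each.

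- At AUC 0.70 and 15/30, sensitivity is 0.73 apparent against 0.63 true, and specificity 0.68 against 0.63.
- Apparent exceeds true in about 80–92% of samples, so this is a bias on average and not a certainty in any one study.
- The smaller group's measure is inflated more. With 50 cases and 150 colonised patients at AUC 0.80, sensitivity is overstated by 0.047 and specificity by 0.016.
- Item 4 does not name a single criterion. Maximising overall accuracy instead of Youden, at AUC 0.80 and 50/50, gives the same Youden excess of 0.081.

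**Item 3, conditional.** The AUC of a single score fixed in advance shows no optimism, averaging 0.70 and 0.80 as assumed. If the AUC comes from a logistic model fitted here, it is optimistic. The table assumes one real predictor of AUC 0.70 and the rest noise, with 1,500 replicates.

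| Predictors | 30/60: apparent vs true AUC | 200/200: apparent vs true AUC |
|---|---|---|
| 3 | 0.72 vs 0.68 | 0.704 vs 0.696 |
| 6 | 0.745 vs 0.66 | 0.71 vs 0.69 |
| 10 | 0.77 vs 0.64 | 0.72 vs 0.68 |

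**The case against.** The strongest objection is that the importance of the bias in this study cannot be known. Every size above rests on assumed group sizes and AUCs. At 200/200 the excess of about 0.034 to 0.042 is no larger than the sampling standard deviation of the apparent Youden index, 0.041 to 0.043. This stands as a limit on the magnitude; it does not change the direction.

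The cut-off is also one of four analysis items, while the stated objective is risk factors and acute exacerbation, and nothing in the documents says the cut-off will guide care. A sentence calling it exploratory would be cheaper. That is fair as to weight, but a label would not show readers how far the accuracy is overstated.

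The SAP is a brief outline, and silence does not prove that validation will be omitted. That too is fair: use of the same patients for selection and reporting is an inference, though the natural reading of the two sections. Validation changes the reported numbers, so it belongs in the plan.

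The item 3 figures depend on a model the SAP does not define and on mostly-noise predictors, which favours large optimism. They are illustrative only; the firm request is that the model be named.

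Finally, the bootstrap corrects only part of the bias, and leaves the most where groups are smallest. This is true and should be stated in the report.

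**Conclusion.** The concern holds. Followed as written, the plan yields sensitivity, specificity and Youden index values for the IgG × image-score cut-off that are on average too high for new patients. Under a binormal marker with AUC 0.70 to 0.80, the Youden excess runs from about 0.13–0.15 at 15/30 down to about 0.04 at 200/200. Confidence is high for the direction; the size in this study cannot be fixed without the group sizes. The AUC in item 3 is affected only if it belongs to a model fitted in these data. The risk-factor comparison is not undermined by this point. The plan should be changed, because the remedy is cheap and needs no new patients or data.

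**What to change.** Add a short internal-validation paragraph to SAP items 3 and 4:

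1. Name the single criterion that defines the cut-off, so the search can be repeated exactly.
2. Draw at least 1,000 bootstrap resamples. In each, repeat the cut-off search and, where a model is fitted, any variable selection and the fit. Apply the result to the original sample. Optimism is the mean of (performance in the resample − performance in the original sample); the corrected value is apparent − optimism.
3. Report corrected sensitivity, specificity and Youden index beside the apparent values for pneumonia, IPA and CPA. Report a corrected AUC only where the model is fitted in these data.
4. Report the bootstrap interval of the selected cut-off, to show how unstable it is.
5. State in item 3 which model or score the AUC refers to.
6. State that the correction is partial and that the cut-off needs confirmation in other patients before use. In the simulation at AUC 0.70 it removed (0.41 − 0.31)/(0.41 − 0.26) = 67% of the excess at 15/30 and (0.32 − 0.29)/(0.32 − 0.28) = 75% at 200/200.

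**Cost.** One SAP paragraph and modest programming in a package that supports resampling; the software line already allows an alternative to SPSS 25.0. No further patients or data are needed. The cut-off part can proceed once the criterion is named; the model part first needs the predictors and selection method written down. The downside is less favourable reported accuracy: Youden lower by about 0.08 to 0.10 at 15/30 (0.55 − 0.47 and 0.41 − 0.31) and by about 0.03 at 200/200 (0.48 − 0.45 and 0.32 − 0.29).
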